- 2) The rate of responders (defined as improvement of LVEF  $\geq$  10% points) with HF medical therapy alone during observation period will be less than 15% *in subjects with CM associated with frequent PVCs*. In contrast to HF medical therapy alone, RFA and AADs will have a responder rate of *at least 35% in the same population*. *Furthermore, RFA will have a greater 1-year response rate when compared to AAD therapy.*
- 3) *RFA will have a lower rate of composite adverse events (worsening NYHA class, HF admission, treatment side effects & complications, and death), arrhythmia burden and a better long-term tolerance than AADs.*
- 4) The prevalence of CM (LVEF  $\leq$  45%) and frequent PVCs ( $\geq$ 10% burden) is largely under recognized in subjects undergoing ambulatory ECG Holters (Part II).

**Methods.** To test our hypotheses, we propose: 1) a clinical pilot study to prove the feasibility of a large-scale multicenter clinical trial (PAPS study) of subjects with probable PVC-CM, and 2) screen near 20,000 consecutive ambulatory ECG Holter monitors of all participating centers to identify all subjects with probable diagnosis of PVC-CM (PVC burden  $\geq$ 10% and LVEF  $\leq$ 45%). The clinical pilot study will enroll between 36-39 subjects with frequent PVCs (burden  $\geq$ 10%) and CM (LVEF  $\leq$ 45%) and randomize them to either: 1) RFA or 2) AADs. Prior to treatment, a baseline cardiac MR will be performed if clinically indicated and be allowed a 3-month observation period. To assess the effects of PVC suppression, we plan to compare changes in LV function, rate of responders (defined above), PVC burden/arrhythmias and clinical/functional status (QOL, HF symptoms and admissions, NYHA class) and adverse events between observation period both PVC suppression strategies (RFA or AAD).

To identify the best PVC suppression strategy, we will perform similar comparisons between RFA and AAD treatment groups during a 12-month follow up using a Prospective Randomized Open, Blinded End-point (PROBE) study design. The treatment regimens will be compared in an intention-to-treat analysis.

Our study is *unique due to its multidisciplinary approach and design* including: 1) observation/control period that allows us to assess for spontaneous improvement of PVCs and/or CM, and 2) active treatment to all subjects, which will allow for easier subject enrollment and retention with minimal drop out.

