**Table 2. Table of Study Procedures**

	3-month Observation			12-month Treatment Phase					
	Obs-V1 Baseline	Obs-V2 2-mo	Obs-V3 3-mo	Tx-V1 Baseline	Tx-V2 1-mo	Tx-V3 3-mo	Tx-V4 6mo	Tx-V5 9-mo*	Tx-V6 12-mo
Timeline in Weeks (range of days)	Week 0 (Day 0)	Week 9 (51-63)	Week 12 (84-96)	Week 12-15 (84-105)	Week 21 (141-153)	Week 26 (176-188)	Week 38 (260-272)	Week 50 (344-356)	Week 64 (441-454)
Informed consent	X								
Inclusion/Exclusion Criteria	X								
Collection of demographic data	X								
Medical History	X								
Physical Exam	X		X		X	X	X	X	X
Functional status/NYHA class	X		X		X	X	X	X	X
QOL Minnesota HF Questionnaire	X		X		X	X	X	X	X
Current / change of medications	X		X		X	X	X	X	X
12-lead ECG	X*	X*	X		X*	X*	X*	X*	X*
Ziopatch	X	X ‡			X €	X	X		X
Echo	X £		X ‡			X	X*		X
BNP / ProBNP levels ESR & CRP	X* £		X*		X*	X*	X*	X*	X*
Urine pregnancy test (if applicable)	X		X	X	X	X	X	X	X
CMR	X*								
TSH (if assigned to amiodarone)			X				X		X
LFT (AST) (if assigned to amiodarone)			X				X		X
Treatment randomization	X								
Initiation of RFA or ADD				X					

Collection of unsolicited AEs	From Obs-Visit 1 until Tx-Visit 6
--------------------------------------	-----------------------------------

Footnote: \*, visit/intervention if clinically indicated.

‡ LVEF results of 2D-echocardiogram and Ziopatch have to be available at the time of Observation Visit 3 (Obs-V3). € If PVC burden >10%, subject should be considered to either adjust antiarrhythmic therapy (AAD group) or second ablation procedure (RFA group) based on their randomization group. ESR, Erythrocyte sedimentation rate; CRP, C-reactive protein. £ Must be done within 150 days of Enrollment Visit (Day 0)

Crossover between PVC suppression strategies is not encouraged. We request that crossover only be considered after 6 months of initiation of treatment, for which an intention-to-treat analysis will be performed. However, if crossover occurs before 6 months of initiation of treatment, subjects will be withdrawn from the study and included in the PVC-CM registry if the subject provided consent.

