**A.1. PVC-CM registry.** This registry will consist of patients that: 1) refuse to participate in the randomized treatment protocol, 2) no longer meet criteria after 3-month observation, 3) crossover before 6 months of treatment initiation, or 4) become pregnant during the study. When allowed by the IRB, informed consent will include an option for participation in this registry as a contingency in case subjects no longer meet criteria, become pregnant, crossover treatment arms or decide to withdraw from the study. A separate informed consent to participate in this registry will be provided only for those patients that refuse participation in the randomized treatment study (main study). Data will be collected at Baseline (day subject refuses enrollment in the randomized study), 6 and 12 months for these subjects. Alternately, subjects included in this PVC-CM registry who screen fail or withdraw early for any reason, will have data collected only by chart review at 6 and 12 months after withdrawing from the study. Data to be collected will include demographics, past medical history, treatment interventions including outcomes and related complications, NYHA functional status, 12-lead ECG, ambulatory ECG Holter including heart rate, PVC burden and arrhythmia burden, echocardiographic data including LVEF, medications and cardiac-related hospital admissions. The purpose of this registry is to assess different treatment options offered to patients with this medical condition in the “real world” as well as the clinical response to these treatments.

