v. *Treatment – Visit 2.* Using appropriate data collection forms, we will ask that sites obtain current medical therapy information, NYHA functional class and Minnesota HF quality of life questionnaire (QOL). 12-lead ECG should be obtained if clinically indicated. A repeat Zio Patch should be placed to re-assess adequate PVC suppression after RFA or initiation of AADs. The local PI and designated site staff will be able to log in to iRhythm’s ZioReports) 3 weeks later to obtain a Zio Patch Report with repeat PVC burden after intervention. If PVC burden is suppressed by more than 80%, intervention is considered successful and the subject should continue with treatment visits as scheduled,

However, if PVC burden does not decrease by more than 80%, intervention is considered a failure. In such a case, the subject should be considered for a second RFA procedure or a different antiarrhythmic drug depending on the randomization group that the subject was assigned (see Section C: Description of the Intervention/treatment). We discourage crossover of treatment arms since this will result in automatic withdrawal from the study. Nevertheless, subjects that withdraw from the study will be included in a PVC-CM registry if the subject provided consent. (described above Section A.1).

**Figure 1.** PAPS study design. A 3-month Observation (Obs) period allows each subject to serve as their own control to assess benefits of PVC suppression. All subjects will be randomized (R) to either RFA or AADs. OMT, optimal medical therapy. QOL, quality of life questionnaire; NYHA, New York Heart Association class; LVEF, LV ejection fraction; Zio, ambulatory ECG Ziopatch Holter, CMR, Cardiac MRI (\*, visit/intervention if clinically indicated).

vi. *Treatment – Visit 3.* Appropriate data collection forms should be used to collect current medical therapy information, NYHA functional class and Minnesota HF quality of life questionnaire (QOL). 12-lead ECG should be obtained if clinically indicated. A transthoracic echocardiogram should be performed to assess LVEF and a copy mailed to the Echo Core laboratory led by [name] III, M.D. A repeat Zio Patch should be placed to re-assess PVC burden. Local PI and designated site staff will be able to log in to iRhythm’s ZioReports 3 weeks later to obtain a Zio Patch Report if desired for any clinical decision.

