vii. *Treatment – Visit 4.* Appropriate data collection forms should be used to collect current medical therapy information, NYHA functional class and Minnesota HF quality of life questionnaire (QOL). 12-lead

ECG should be obtained if clinically indicated. If clinically indicated, a transthoracic echocardiogram should be performed to assess LVEF and a copy mailed to the Echo Core laboratory led by [name] III, M.D. A repeat Zio Patch should be placed to re-assess PVC burden. The local PI and designated site staff will be able to log in to iRhythm's ZioReports 3 weeks later to obtain a Zio Patch Report if desired for any clinical decision. In addition, subjects in the antiarrhythmic (AAD group) will require a follow-up TSH and LFTs if amiodarone is part of the current treatment.

viii. *Treatment – Visit 5.* Using appropriate data collection forms, we will ask that sites obtain current medical therapy information, NYHA functional class and Minnesota HF quality of life questionnaire (QOL). 12-lead ECG should be obtained if clinically indicated. If a transthoracic echocardiogram is performed for any reason prior to this visit, we will ask that sites mail a copy to the Echo Core laboratory ([name] III, M.D.).

ix. *Treatment – Visit 6.* Using appropriate data collection forms, we will ask that sites obtain current medical therapy information, NYHA functional class and Minnesota HF quality of life questionnaire (QOL). 12-lead ECG should be obtained if clinically indicated. A final, transthoracic echocardiogram should be performed to obtain assessment of LVEF and images should be sent to the Echo Core laboratory ([name].). A repeat Zio Patch should be placed to re-assess PVC burden. The local PI will be able to log in to iRhythm's ZioReports to obtain a Zio Patch Report if thought to be needed for treatment decisions. In addition, subjects in the antiarrhythmic (AAD group) will require a follow-up TSH and LFTs if amiodarone is part of the current treatment.

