#### **E. Primary and secondary outcome measures.**

*The outcomes are divided in primary and secondary end-points (Table 3).*

*The primary end-points will consist of:*

1. *Improvement of LVEF after PVC suppression at 12-month follow-up.* This is chosen as primary-end point due to the known prognostic value of LVEF. The lower the LVEF, the higher the risk of sudden cardiac death and heart failure. This will compare the overall improvement or change in LVEF between RFA and AAD groups. This end-point will support that either RFA or AADs have an overall better outcome due to significant improvement of LV function with potential impact on morbidity and mortality associated with PVC-CM.

2. *Responders to PVC suppression strategy at 12-month follow-up* (See rationale under Section “Definitions” in 3rd paragraph of Aim 2). Assessment of the number of responders (delta LVEF  $\geq$  10%) after PVC suppression strategies (RFA or AADs) will assess the effectiveness of RFA and AADs to reverse or improve cardiomyopathy induced by frequent PVCs. Evidence that either RFA or AADs is superior to improve or even reverse LV dysfunction in subjects with high burden PVCs could have significant impact of morbidity and mortality including future heart failure and ventricular arrhythmias, and also may avoid ICD implantation.

*The secondary end-points will consist of:*

1. *Efficacy of RFA vs AADs groups to achieve successful PVC suppression at 12-month follow-up, defined as a reduction of PVC burden  $\geq$ 80% (regardless of LVEF change). Understanding the success rate of PVC suppression between RFA and AADs will help better determine the best treatment to those subjects with high PVC burden.*

2. *Composite end-point of adverse events at 12-month follow-up, including worsening in NYHA functional class (I-IV), number of HF and cardiac-related admissions, RFA complications and AAD adverse effects and cardiovascular death.*

This adverse event composite end-point is chosen to understand the overall complications and adverse effects/events related to RFA and AADs. Worsening of NYHA functional class will be defined as when/if the subject’s functional status worsens by one NYHA class. Hospital admissions will be defined as any visit to ED or hospital admissions related only to a cardiovascular event such as heart failure, angina, pre/syncope and palpitations.

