### **H. Limitations**

The following limitations may arise during the development of this project:

1. Subjects with progression from mild and moderate to severely symptomatic PVCs (incapacitating palpitations and dizziness) will be encouraged to complete the 3-month observation period since PVC suppression will initiate immediately thereafter. Subjects are excluded if symptoms preclude completion of the 3-month observation.
2. Limited or poor suppression of PVC suppression in randomized treatment (RFA or AAD) arm. These subjects are encouraged to remain on the assigned arm. However, crossover to the alternate treatment arm can be considered after 6 months only if considered medically indicated. If crossover were to occur before 6 months, immediate notification and final evaluation with echocardiogram and ambulatory ECG Holter monitor (Zio Patch) should be obtained prior to crossover, and the subject will be excluded from study and followed in a PVC-CM registry if consent was provided (described above Section A.1).
3. PVC variability or spontaneous resolution of PVCs may limit pre vs post procedure comparison. PVC burden has significant temporal variability and it may be a major limitation in the study of arrhythmias. Schmidt demonstrated that an 80% absolute reduction of PVC burden is required to show a true drug effect. To minimize daily PVC variability, PVC evaluation in this study will be performed using a 2-week ambulatory ECG Holter monitor (Zio Patch, IRhythm, Inc.) which is shown to be a better indicator of long-term PVC burden.
4. LV function assessment in ventricular bigeminy. Assessment of LVEF during frequent PVCs represents a challenge for all imaging modalities. Modified acquisition and post-processing methods have been developed to correct for R-R interval variability expected with frequent PVCs. In the event that the subject has persistent ventricular bigeminy at the time of the scheduled echocardiography, the LV function assessment should be postponed for a few hours or a later date when PVCs are less prominent (at least ventricular quadrigeminy).

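### Subjects who cross over before 6 months are withdrawn before the Week-64 echocardiogram, so the promised intention-to-treat comparison has no clearly scheduled 12-month outcome for them

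*Combined protocol and SAP*

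**What the plan says.** **Analysis principle.** The Abstract and Specific Aims state, without restriction: "The treatment regimens will be compared in an intention-to-treat analysis". Randomisation is at the baseline visit, Week 0 (Part I, Section A, Definitions; Table 2; Section B, Observation Visit 1).

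**Primary endpoints.** Section E names "Improvement of LVEF after PVC suppression at 12-month follow-up" and the responder rate at the same time point. Both need the Week-64 visit (Treatment Visit 6): "A final, transthoracic echocardiogram should be performed to obtain assessment of LVEF and images should be sent to the Echo Core laboratory". Section C (c.3) has the images read by a cardiologist blinded to arm.

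**Crossover.** The text under Table 2 asks that "crossover only be considered after 6 months of initiation of treatment, for which an intention-to-treat analysis will be performed". For earlier crossover it says: "However, if crossover occurs before 6 months of initiation of treatment, subjects will be withdrawn from the study and included in the PVC-CM registry". Registry entry depends on consent. The rest of Section A, including A.1, repeats this. Section B, Treatment Visit 2, states no time limit: "We discourage crossover of treatment arms since this will result in automatic withdrawal from the study". Section H, item 2, says of early crossovers that "echocardiogram and ambulatory ECG Holter monitor (Zio Patch) should be obtained prior to crossover, and the subject will be excluded from study". Section D rules out crossover before 6 months except where the subject's welfare makes it critical.

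**Data after withdrawal.** Under A.1, registry subjects who withdraw early "will have data collected only by chart review at 6 and 12 months after withdrawing from the study". Section F, on spontaneous recovery, speaks of six-monthly LVEF for registry subjects, in a paragraph about subjects who no longer qualify at Week 12.

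**Statistical section.** Section I names no analysis set, gives no rule for missing 12-month LVEF, and does not say whether registry or pre-crossover values enter the comparison.

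**The concern.** Removing randomised subjects because of something that happens after randomisation is not intention to treat. The subjects removed are also unlikely to be a random sample of their arm. Treatment Visit 2 and Section H raise crossover in the setting of failed or poor PVC suppression, and Section D in the setting of the subject's welfare, so loss is tied to outcome or tolerance.

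Those who remain therefore give a 12-month LVEF change and responder rate that answer no clear question. They do not describe the arms as assigned, and they do not describe what full adherence would give, because the retained group is selected. Section F (rate of responders) and the sample size justification use the pilot to size the full trial, so these are the figures that would be carried forward, with no scheduled data from which to judge the distortion.

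**Working it through.** **1. What an early crossover contributes at 12 months.** Let crossover occur t months after treatment starts, with t below 6.

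| Source | Timing from treatment start | Scheduled echo? | Core-lab reading? |
|---|---|---|---|
| Treatment Visit 6 (Week 64) | 12 months | Yes | Yes, but the subject has been withdrawn |
| Evaluation before crossover (Section H) | up to t, so before month 6 | Yes | Not stated |
| Registry chart review (A.1), with consent | t + 6 and t + 12, so months 6–12 and 12–18 | No | Not stated |
| Registry LVEF every 6 months (Section F) | unclear for this group | Conflicts with A.1 | Not stated |

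Chart review may find a clinical echocardiogram near month 12, but nothing schedules one or brings it into the comparison of arms.

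**2. The plan's own sample size.** Inputs from the sample size justification: baseline LVEF 25% (SD 5), 12-month LVEF 40% and 35% (SD 10), within-subject correlation 0.25, power 0.80, alpha 0.05 (taken as two-sided), 10% random dropout.

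- SD of change = √(5² + 10² − 2 × 0.25 × 5 × 10) = √100 = 10.
- n per arm = 2 × (1.96 + 0.8416)² × 10² / 5² = 62.8, so 63.
- Total = 126 / 0.9 = 140, as stated.

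**3. Illustration of the distortion.** Mean changes are 40 − 25 = 15 (RFA) and 35 − 25 = 10 (AAD). The documents give no crossover rate, so three values are assumed: a share q = 0.20 of the AAD arm crosses early, none of the RFA arm does, and the driver of crossover correlates r = 0.5 with LVEF change. With φ(z) the normal density at the 20% point, 0.280:

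- Retained AAD mean = 10 + r × 10 × φ/(1 − q) = 10 + 5 × 0.280/0.80 = 11.75.
- Crossovers' mean had they stayed = 10 − 5 × 0.280/0.20 = 3.0.
- Difference after withdrawal = 15 − 11.75 = 3.25.
- Intention-to-treat difference = 15 − (0.8 × 11.75 + 0.2 × m), where m is the crossovers' mean change at 12 months.

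| m | ITT difference | Withdrawal minus ITT |
|---|---|---|
| 3 (switching changes nothing) | 5.0 | −1.75 |
| 10 | 3.6 | −0.35 |
| 15 | 2.6 | +0.65 |

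The gap is q × (m − 11.75), so it vanishes at m = 11.75 and changes sign there.

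Under the same model the AAD responder rate (change of at least 10 points) is about 57% among those retained. Among crossovers it is 22%, 50% or 69% for the three values of m, so the intention-to-treat rate is 0.8 × 57% + 0.2 × (22%, 50% or 69%) = about 50%, 56% or 59%.

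**4. Pilot precision.** The base of 30 in the sample size justification gives about 15 treated per arm, since the extra 6–9 subjects cover improvement during observation. The 95% half-width is 1.96 × 10 × √(2/15) = 7.2 points, before dropout.

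**The case against.** **Early crossover is meant to be rare.** This stands. Section D makes it an exception, and failed suppression is first handled within the assigned arm (Table 2 footnote, Treatment Visit 2, Section D). The 20% above has no source in the documents. At 5% crossover in the AAD arm only, with r from 0.3 to 0.7 and m at the stay value, 10 or 15, the gap runs from −0.76 to +0.23 points.

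**Intention to treat may be meant only for late crossovers.** The sentence under Table 2 can be read so, but the Abstract and Specific Aims carry no such limit. If one was intended, the passages still need reconciling.

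**The registry may supply the outcome.** Section F's six-monthly LVEF refers the reader to A.1, which includes early crossovers. But its paragraph concerns Week-12 screen failures, and A.1 limits early withdrawals to chart review. It does not clearly fill the gap. Equally, a reader might infer that these subjects have no LVEF at all after crossover. The documents do not support that either, since chart review may retrieve a value.

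**It is a pilot.** Aim 1 is feasibility, and the Data Sharing Plan disclaims conclusions about the relative benefit of the strategies. Counts of enrolment, crossover and withdrawal are unaffected. The own-control comparison at 3 months is less affected, because Table 2 schedules an echocardiogram then and Section H asks for one before crossover. What remains exposed is the set of 12-month planning estimates.

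**Random dropout.** A reader might set the 10% random dropout against this informative loss as a flaw in the pilot's analysis. That assumption belongs to the 140-subject calculation for the full-scale trial, and the pilot analysis makes no such statement.

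**Conclusion.** The point holds on the text. The plan promises an unrestricted intention-to-treat comparison and then withdraws a group of randomised subjects before the visit that supplies both primary endpoints. It provides no clearly scheduled replacement and no analysis rule.

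Size and direction are not known. A reader might infer from the illustration that the rule understates the advantage of RFA. The documents do not support that: the sign depends on which arm crosses and on the response after switching, and the 3.25 rests wholly on the assumed 20%, r = 0.5 and AAD-only crossover. With a half-width of about 7.2 points (assuming about 15 treated per arm), noise exceeds every gap shown. The case for change is that the 12-month estimates handed to the full trial should answer a defined question. It should be fixed, but it does not threaten the feasibility aim.

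**What to change.** 1. In the text under Table 2, the rest of Section A including A.1, Section B (Treatment Visit 2) and Section H (item 2), separate crossover from end of follow-up. Keep early crossovers in their assigned arm, collect the Week-64 echocardiogram and Zio Patch already in Table 2 unless consent is withdrawn, and analyse them as randomised.
2. In Section I, state this analysis set and how a Week-64 LVEF that is still missing will be handled. Add a sensitivity analysis using the pre-crossover echocardiogram.
3. Reconcile the text under Table 2, Treatment Visit 2, Section D and Section H on the consequence of crossover, and A.1 with Section F on registry LVEF. None of this changes when crossover is clinically allowed.

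**Cost.** Protocol wording, plus about 2–5 extra Week-64 echocardiogram and Zio pairs if 10–30% of one arm of about 15 crosses early (1.5 to 4.5 subjects). Section H, item 5, notes limited funds, so these need a budget line. The intention-to-treat effect will include the treatment crossed to, and withdrawal will no longer serve as the deterrent to crossover that Treatment Visit 2 makes of it.

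The conflicting statements on when randomisation occurs, and the registry follow-up of Week-12 screen failures, are separate matters.

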Every effort will be made to have females enter this study. Medically accepted birth control is required to enter this study. This may include, but is not limited to, birth control pills, IUD's, condoms, diaphragms, implants, being surgically sterile, or being in a post-menopausal state. However, no birth control method completely eliminates the risk of pregnancy and potential risk of miscarriage, birth defects, other medical complications or unforeseen risks to subject or to the unborn baby (i.e. embryo or fetus) is possible if pregnancy occurs during the study. Any female of childbearing age must have a negative pregnancy test before entering the study.

A pregnancy test will be obtained on females of childbearing age that are assigned to the RFA treatment prior to procedure due to fluoroscopy exposure. In contrast, a pregnancy test will be performed on a monthly basis on those randomized to the antiarrhythmic treatment arm to confirm the lack of pregnancy throughout the 12-month follow up. If a female on the antiarrhythmic arm becomes pregnant during the 12-month follow up we will consider stopping antiarrhythmics and the subject will be withdrawn from the study.

Thus, subjects that no longer meet criteria after the 3-month observation period, those that crossover before 6 months of treatment initiation or become pregnant during the study will be included in the PVC-CM registry if the subject provided consent. Subjects that refuse participation in this portion of the study (Part I) will also be included in the PVC-CM registry if they provide consent.

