### **Risk Benefit assessment**

All PVC suppression strategies (RFA and AADs), proposed in this grant application are approved by the Heart Rhythm Society and FDA for the treatment of ventricular arrhythmias, respectively. Subjects assigned to the RFA arm may have a small risk of minor or major complications related to RFA of PVCs. However, these risks associated with RFA of PVCs are acceptable and RFA of PVCs continues to be performed in clinical practice even though there is limited data to support benefit from this intervention. Risks associated with RFA are small (1-2%) including but not limited to stroke, myocardial infarction, coronary artery injury, bleeding, cardiac tamponade, pneumothorax, atrioventricular block with subsequent need for permanent pacemaker, and even death. Similarly, antiarrhythmic drugs (AAD) may have long-term risks/adverse effects based on the antiarrhythmic chosen (e.g. amiodarone has significant long-term effects including lung disease such as decrease in lung diffusion capacity, optical neuritis, abnormal thyroid and liver function, and pro-arrhythmic effects; see Section C in Protection of Human Subjects document for details). Yet, these treatment options are currently standard of care frequently offered to this subject population with known complications and these adverse events. To minimize the potential risks with AADs, all subjects should be considered for additional safety laboratory analyses during treatment as recommended per guidelines based on AAD chosen (amiodarone - TSH, LFTs, PFTs, eye exam).

A pregnancy test will be obtained on females of childbearing age that are assigned to the RFA treatment prior to procedure due to fluoroscopy exposure. In contrast, a pregnancy test will be performed on a monthly basis on those randomized to the antiarrhythmic treatment arm to confirm the lack of pregnancy throughout the 12-month follow up period. If a female on antiarrhythmic arm becomes pregnant during the 12-month follow up period, we will consider stopping antiarrhythmics and the subject will be withdrawn from the study.

The IRB should be notified of any serious adverse events (SAE) within 24 hours of such event or knowledge of the event. Additionally, the PAPS National Research Coordinator should be notified within 24 hours of the event or knowledge of the event. The investigator must decide whether each incident meets the definition of a SAE.

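### Pregnancy testing in the AAD arm is monthly in the protocol text but tied to visits in Table 2, so the documents do not give one schedule per arm

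*Combined protocol and SAP*

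**What the plan says.** **Text.** Two places set the frequency by arm. In Study Design Part I, Section A, after Table 2, the RFA arm is tested before the procedure because of fluoroscopy, while for the other arm "a pregnancy test will be performed on a monthly basis on those randomized to the antiarrhythmic treatment arm". Section J, Risk Benefit assessment, repeats the rule: "a pregnancy test will be performed on a monthly basis on those randomized to the antiarrhythmic treatment arm to confirm the lack of pregnancy". Both apply it through the 12-month follow-up. Both add that, if a woman in the AAD arm becomes pregnant, stopping the drug will be considered and she will be withdrawn.

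**Table 2.** The row "Urine pregnancy test (if applicable" (closing bracket omitted) is marked at Obs-V1, Obs-V3 and each of Tx-V1 to Tx-V6. It has no between-visit entry, no footnote and no split by arm. The TSH and LFT rows of the same table do carry a condition on assigned treatment.

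**Standing of the table.** Section G (Data collection) refers to Figure 1 and Table 2 for all procedures and tests in the observation and treatment periods. Section B (Scheduled Visits) and Section C (Clinical Assessment and tests) also send the reader there. The visit-by-visit instructions in Section B do not mention a pregnancy test.

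**The concern.** A site can complete every pregnancy test marked in Table 2 and still miss the monthly commitment made twice in the text. Nothing in the table or the visit instructions alerts it to the shortfall.

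The stake is patient safety. The text itself warns that contraception does not remove the risk of pregnancy and names possible harm to the mother and the unborn child. In the AAD arm a positive test triggers two actions: consideration of stopping the drug, and withdrawal. The interval between tests determines how late those actions could come.

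The arms are also treated differently in the two places. The text contrasts a pre-procedure test (RFA) with monthly tests (AAD). The table applies one visit-based pattern to both.

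**Working it through.** The plan states no figure for the interval between tests, so there is none to reproduce. The check takes the day windows in Table 2 and compares the intervals they allow with a month.

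**Inputs (Table 2, treatment phase)**
- Tx-V1: "Week 12-15 (84-105", that is days 84-105
- Tx-V2: "Week 21 (141-153", days 141-153
- Tx-V3: "Week 26 (176-188", days 176-188
- Tx-V4: "Week 38 (260-272", days 260-272
- Tx-V5: "Week 50 (344-356", days 344-356; its column heading carries the asterisk for visits held only on clinical indication
- Tx-V6: week 64, days 441-454

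**Formulas**
- Shortest gap = earliest day of the later visit − latest day of the earlier visit
- Longest gap = latest day of the later visit − earliest day of the earlier visit

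| Interval | Shortest (days) | Longest (days) | Weeks |
|---|---|---|---|
| Tx-V1 to Tx-V2 | 141 − 105 = 36 | 153 − 84 = 69 | 5.1-9.9 |
| Tx-V2 to Tx-V3 | 176 − 153 = 23 | 188 − 141 = 47 | 3.3-6.7 |
| Tx-V3 to Tx-V4 | 260 − 188 = 72 | 272 − 176 = 96 | 10.3-13.7 |
| Tx-V4 to Tx-V5 | 344 − 272 = 72 | 356 − 260 = 96 | 10.3-13.7 |
| Tx-V5 to Tx-V6 | 441 − 356 = 85 | 454 − 344 = 110 | 12.1-15.7 |

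Only the Tx-V2 to Tx-V3 interval can be as short as a month.

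**Number of tests after treatment start**
- Table 2: Tx-V2 to Tx-V6, so five. The test at Tx-V1 is left out because treatment starts at that visit.
- Monthly rule: Tx-V1 to Tx-V6 spans 441 − 105 = 336 to 454 − 84 = 370 days. At 30.44 days per month this is 336/30.44 = 11.0 to 370/30.44 = 12.2 months, so about 11 to 12 tests.

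**If Tx-V5 is not held**
- Tx-V4 to Tx-V6: 441 − 272 = 169 to 454 − 260 = 194 days (24.1-27.7 weeks).
- Only the asterisk in Table 2 supports this case. The Synopsis follow-up schedule lists week 50. Section B gives data-collection instructions for Tx-V5 without making the visit conditional. Section D counts five follow-up visits in each arm, and for the RFA arm numbers them 2 to 6.

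**RFA arm**
- The Tx-V1 mark can serve as the pre-procedure test that the text asks for. The table's later marks go beyond the text for this arm but break no rule in it.

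**The case against.** The strongest reply is that the two places do not strictly contradict each other. Table 2 is a grid of scheduled visits and has no column for a test between visits. It does not forbid extra tests, and the monthly rule is worded as a requirement, appears twice, and stands once shortly after the table. A site that reads both can satisfy both. No passage says that the table overrides the text, and Section C mentions a Manual of Operations that may hold fuller instructions and is not among the documents reviewed. All of this stands, and it is why the gaps above are stated for a site that follows only the table.

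It does not remove the mismatch. Section G presents the table and figure as the outline of all tests, and a footnote could have carried the monthly rule. Limiting the row to women to whom the test applies restricts who is tested; it does not add test dates.

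It is also fair to cite the other safeguards. Accepted contraception and a negative test are conditions of entry, and pregnancy is an exclusion. The Data Safety Monitoring Plan tells subjects to call about anything unusual, and monthly emails or calls are planned for retention. The arm has only about 19-20 subjects, and just the women of childbearing age among them are affected. These points limit the consequence without settling which schedule applies.

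Two stronger readings are tempting. A reader might infer that the plan permits about half a year without a test. That requires Tx-V5 to be skipped, and the Synopsis, Section B and Section D all treat it as a scheduled visit. A reader might also infer that the retention result is affected, because pregnancy leads to withdrawal. Later detection would mainly shift the date of a withdrawal; the documents give no expected number of pregnancies and nothing that shows an effect on retention.

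**Conclusion.** The inconsistency is real and should be corrected. The text commits to monthly tests in the AAD arm and a pre-procedure test in the RFA arm, whereas Table 2 gives one visit-based pattern for both.

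For a site working from the table alone, the shortfall in the AAD arm is five tests against about 11 to 12, with the three late intervals running from about 10 to 16 weeks. These figures assume that all visits take place within their windows, that Tx-V5 is held, and that no test is done between visits. The 169-194 day interval is conditional on Tx-V5 not being held.

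The matter is one of patient safety and consistent instructions to sites. The number of women affected is not stated and is probably small. No effect on retention, on any endpoint or on any estimate is claimed.

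**What to change.** Reconcile Section A (text after Table 2) and Section J (Risk Benefit assessment) with Table 2, so that all three state the same pregnancy-testing schedule for each arm. A separate row per arm, or a footnote to the existing row, would be enough on the table side; if the text is what changes, both sections need the same edit. Which schedule is right is for the sponsor and investigators to decide, and this review takes no position on it.

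The cost is a table row or footnote, or a wording change. No change to the design, sample size or analysis is needed.
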